In December 2017, a trial compared a chewed sublingual form of ticagrelor to standard pill form in patients with STEMI. It also showed more rapid absorption and platelet inhibition within hours of drug administration. To our knowledge, our study will be the first to compare platelet reactivity in non ST segment elevation acute coronary syndrome (NSTE-ACS) and patients with stable CAD undergoing PCI who received chewed ticagrelor.

Specific Aims:

To compare the effect of ticagrelor chewed pills with the effect of equal dose of integral pills in decreasing platelet reactivity and adverse event rates in all patients being treated for NSTE-ACS and stable coronary artery disease, undergoing percutaneous coronary intervention.

Primary objective:

Determine platelet inhibition at baseline, and early at 1 hour and 4 hours after loading dose.

Secondary objective:

Assess major adverse cardiac and cerebrovascular event (MACCE) rate at 30 days and 1 year.

1. Death;
2. Repeat myocardial infarction;
3. Need for urgent revascularization;
4. Cerebrovascular accident;
5. Rate of stent thrombosis and in-stent stenosis at 30 days and 1 year;
6. Bleeding: Defined as major, minor, or minimal bleeding based on TIMI criteria.

Hypothesis:

Chewed ticagrelor pill is superior to integral pill in decreasing platelet reactivity.

Primary Outcome Measures:

Residual platelet reactivity by Platelet Reactivity Units (PRU) VerifyNow 1 hour and 4 hours after ticagrelor loading dose (LD) and percent of patients with a high residual platelet reactivity (PRU > 208) 1 hour and 4 hours after ticagrelor LD.

Secondary Outcome Measures:

1. Bleeding events: Major, minor, minimal bleeding (TIMI criteria) events.
2. Occurrence of dyspnea and/or symptomatic bradycardia.
3. Major adverse cardiac and cerebrovascular event (MACCE) rate: Death, Myocardial infarction, Stent Thrombosis, Urgent revascularization, Cerebrovascular accident at 30 days and 1 year.

STUDY DESIGN

This will be an interventional study to evaluate the superiority of chewed ticagrelor in comparison to integral pill form. Superiority will be defined as a reduction of platelet reactivity in both groups undergoing PCI.

Study population will include 132 patients. They will be stratified into 2 groups: Patients with NSTEMI-ACS and patients with stable coronary artery disease (CAD) undergoing coronary angiography for non-urgent reasons.

Inclusion criteria:

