- 4. Patients presenting with NSTEMI-ACS or stable CAD undergoing coronary angiography for urgent or non-urgent reasons.

Exclusion criteria:

1. Age <18 years or Age >90 years;
2. Known coagulopathy, bleeding diathesis, or active bleeding;
3. Known chronic therapy with clopidogrel, prasugrel, or ticagrelor;
4. Known history of intracranial bleed or intracranial neoplasm;
5. Suspected aortic dissection;
6. Severe hemodynamic instability, cardiogenic shock;
7. Life expectancy <1 year;
8. Known severe liver or renal disease (CrCl < 30, or dialysis dependent);
9. Taking drugs known to interfere with CYP3A4 metabolism (Azoles, Clarithromycin, Ritonavir, Saquinavir, Nelfinavir, Indinavir, Atazanavir);
10. Any use of GP IIb-IIIa inhibitors 48-hours before the procedure or any use during the procedure;
11. Any use of Cangrelor during or after the procedure;
12. Hemoglobin <10 g/dL, PLT <80x10⁹/L;
13. Pregnant or lactating females;

14. Known allergy to study medication;
15. Fibrinolytic use within past 48 hours;
16. Inability to give consent;
17. Known sick sinus syndrome (SSS) or high degree AV block without pacemaker protection.

Written informed consent:

Patients presenting for both urgent and elective left heart catheterization will be consented by the personnel delegated by the investigator before any study-related activity.

Randomization:

Patients will be randomized prior to PCI. Patients from each strata (NSTE—ACS, and patients with stable CAD) will be randomized in a 1:1 fashion to receive a loading dose of 180mg ticagrelor in integral pill form (swallowed) or chewed form.

Study procedures:

Patients admitted to the inpatient cardiology service with NSTE-ACS meeting eligibility criteria are often treated medically before reaching the catheterization suite for coronary angiography and possible percutaneous coronary intervention. These patients often receive the loading dose of 180mg ticagrelor on the medical floor. In order to enroll these patients, the baseline PRU level blood draw, can be obtained on the floor before that loading dose is administered. The subsequent 1-hour and 4-hour blood draws can be obtained on the medical floor or in catheterization suite.

[figure not shown]

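### Exclusion 3 bars only chronic oral P2Y12 therapy, so a patient given a one-off non-study P2Y12 dose earlier in the episode can be randomised with PRU already lowered, which dilutes the chewed-versus-integral contrast

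*Combined protocol and SAP*

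**What the plan says.** In the combined protocol and SAP, Exclusion criteria, item 3 reads "Known chronic therapy with clopidogrel, prasugrel, or ticagrelor". It gives no look-back window and does not mention a single or recent dose.

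Other antithrombotic drugs are treated differently in the same list:
- Item 10: "Any use of GP IIb-IIIa inhibitors 48-hours before the procedure or any use during the procedure".
- Item 15: "Fibrinolytic use within past 48 hours".
- Item 11: "Any use of Cangrelor during or after the procedure". This sets no limit on use before the procedure.

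The visible inclusion text is "Patients presenting with NSTEMI-ACS or stable CAD undergoing coronary angiography for urgent or non-urgent reasons". It does not require that the patient be free of P2Y12 inhibitors.

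Under Study procedures, NSTE-ACS patients "are often treated medically before reaching the catheterization suite for coronary angiography and possible percutaneous coronary intervention". The next sentence adds: "These patients often receive the loading dose of 180mg ticagrelor on the medical floor". The section then says that the baseline PRU sample can be taken on the floor ahead of that dose. The arm table places the loading dose after the baseline draw in both arms.

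The primary outcomes are PRU at 1 and 4 hours after the loading dose, and the percentage of patients above 208 at those times.

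The Data collection table lists prior aspirin, beta-blockers and statins, but no prior P2Y12 inhibitor. The Schedule of events has a general concomitant-medication entry at Visit 1. The Statistical Analysis section names no analysis set defined by prior P2Y12 exposure.

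**The concern.** PRU measures the pathway that these drugs block. A patient who received a non-study dose of clopidogrel, prasugrel or ticagrelor before the baseline draw may start with lowered PRU in either arm. That leaves less room for the way the study tablet is taken to show a difference. The hypothesis is that chewing lowers platelet reactivity more than swallowing whole, measured early, so such patients carry less information on the question and may carry none.

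The protocol expects NSTE-ACS patients to be treated before catheterisation, so this stratum is where the gap could matter. At stake is power. A null result could not be separated from dilution if prior exposure had been neither excluded nor recorded.

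**Working it through.** **1. Can the plan's own figure be reproduced?** No. The Study Design section gives 132 patients, without a power, effect size, SD or event rate. Everything below is therefore for scale only.

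**2. Does any criterion cover a one-off prior P2Y12 dose?** I read all 17 exclusions and the visible inclusion text.

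| Drug class | Criterion | Prior single dose excluded? |
|---|---|---|
| Oral P2Y12 inhibitors | Item 3, chronic therapy only | No |
| GP IIb-IIIa inhibitors | Item 10, 48-hour look-back | Yes |
| Fibrinolytics | Item 15, 48-hour look-back | Yes |
| Cangrelor | Item 11, during or after the procedure | Not before it |

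The drafters wrote look-back windows elsewhere. The study drug's own class has none.

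**3. Does the order of the baseline draw close the gap?** Only for the study dose. Study procedures and the arm table put the baseline draw before the floor or catheterisation-laboratory load. They do not deal with a different drug given earlier, or with a dose given before the patient reached the floor.

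**4. Dilution.** Inputs are N = 132 and 1:1 allocation, so 132 / 2 = 66 per arm. The pre-exposed share f is not in the documents, so 5% to 20% is an assumed range. Assume also that exposed patients carry no arm difference.

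- Observed difference = (1-f) x true difference.
- Effective N = 132 x (1-f)^2.

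For a power scale, I assume two-sided 5% and choose the effect that gives 80% power at 66 per arm: d = (1.960 + 0.842) x sqrt(2/66) = 0.488 SD.

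| f | Effective N | Power, no effect left | Power, half the effect left | Total N to hold 80%, no effect left |
|---|---|---|---|---|
| 0% | 132 | 80% | 80% | 132 |
| 5% | 132 x 0.9025 = 119 | 76% | 78% | 148 |
| 10% | 132 x 0.81 = 107 | 71% | 76% | 164 |
| 20% | 132 x 0.64 = 84 | 61% | 71% | 208 |

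**5. If exposure is confined to one stratum.** Overall f = (share of patients in the stratum) x (share exposed within it). Stratum sizes are not stated. If NSTE-ACS were half the sample (assumption), 20% exposed within it gives 0.5 x 0.20 = 10% overall. The effective N is then 107, not 84.

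**6. What the formula leaves out.** Zero remaining effect is the extreme case for dilution of the difference. It is not a strict ceiling on lost power, because a subgroup with lower PRU also widens the spread. If exposed patients averaged 1 SD lower (assumption), the SD becomes sqrt(1 + f(1-f)). That is 1.044 at f = 10% and 1.077 at 20%, and power falls to 68% and 55%. Adjusting for baseline PRU could recover part of that spread, but not the lost difference.

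**7. PRU above 208.** Assume rates of 50% and 25%, with every exposed patient below 208. The difference shrinks from 25 points to 22.5 at f = 10% and 20 at f = 20%. Power at 66 per arm goes from 85% to 79% and 71%.

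**The case against.** **Floor loading.** A reader might take the sentence on floor loading as proof that patients arrive already loaded with non-study ticagrelor. The documents do not support that. The section goes on to explain how to enrol these patients by drawing the baseline first, and the arm table lets a floor nurse give the study dose after that draw. The natural reading is one load, the study load. What remains is that Study procedures says the draw can come first, while the arm table makes the order definite.

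**Bias.** A reader might infer that the gap hides the treatment effect or biases the comparison. Randomisation is 1:1 within stratum, so prior exposure is not expected to favour either arm. The harm is attenuation, which works against the superiority hypothesis and does not create false positives.

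**A second loading dose.** A reader might also infer that the eligibility rules were meant to prevent a second load and fail to do so. The documents state no such intent and describe no such pathway.

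**Frequency.** The documents mention no one-off clopidogrel or prasugrel dose and no load in an emergency department or referring hospital. The statement about prior medical treatment names no drug. The share f could be close to zero. This objection stands.

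**Missing text.** The visible inclusion list begins at item 4. Earlier items may have been lost when the PDF was read, or the numbering may be an artefact. A lost item could bear on this point, which limits confidence.

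**Partial safeguards.** Baseline PRU is measured in every patient and is one of the time points in the planned regression model. Concomitant medications are recorded at Visit 1. Exposure may therefore be detectable, but the plan does not say that it will be identified or used in the analysis.

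**Conclusion.** The gap in wording is real. As written, the visible criteria admit a patient with a recent one-off non-study P2Y12 dose, and neither the listed data fields nor the analysis plan deals with that patient. The consequence is dilution of both primary measures and lost power, with no expected tilt toward either arm.

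The size cannot be fixed from the documents. An effective sample of 119, 107 or 84 rests on an assumed f of 5%, 10% or 20%, spread over all 132 patients and with no remaining effect. The loss is smaller if some effect remains or if only NSTE-ACS patients are affected. It is larger if exposed patients also widen the spread of PRU and the analysis does not adjust for baseline.

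This is worth correcting but does not by itself undermine the trial. Confidence is moderate, because f is unknown and the inclusion list may be incomplete.

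**What to change.** 1. Extend exclusion 3 to any non-study P2Y12 inhibitor dose within a window before the baseline PRU draw. The sponsor sets the window. Check it in the Visit 1 concomitant-medication review.
2. Reconcile Study procedures, where the baseline draw is permissive, with the arm table, where the loading dose follows it.
3. Add prior P2Y12 exposure (drug and time) to the Data collection table.
4. Keep any patient found after randomisation to have been exposed in the main analysis, and pre-specify a sensitivity analysis in unexposed patients. Exposure precedes randomisation, so the subset keeps a randomised comparison, provided that it is classified from the records without regard to arm.

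The cost is a short amendment, one extra data field and one extra analysis. Some NSTE-ACS patients become ineligible, so recruitment in that stratum is slightly slower.

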Patients scheduled to undergo and elective (non-urgent) coronary angiography for stable CAD who meet eligibility criteria will have blood drawn for a baseline PRU level prior to administration of the study drug. After the procedure, two subsequent blood draws will be taken at precise times: 1 hour +/-60 minutes, and 4 hours +/- 90 minutes after loading dose administration. All other procedures are considered standard of care.

Arm	Intervention/Treatment
Arm One: Chewed ticagrelor pills (Loading dose 180mg)	Drug: Ticagrelor chewed pills. The loading dose will be administered as soon as possible by hospital floor nurse or Catheterization Lab staff after a baseline PRU level is drawn. Patients will be asked to

	chew and swallow followed by 25-50mL of water.
Arm Two: Integral pill form of ticagrelor (Loading dose 180mg)	Drug: Ticagrelor integral pills. The loading dose will be administered as soon as possible by hospital floor nurse or Catheterization Lab staff after a baseline PRU level is drawn. and before the end of the PCI . Patients will swallow the loading dose followed by 25-50mL of water.

Subject will have orders to continuing ticagrelor during admission status. After the 4th hour blood draw the primary outcome will be complete. Patients will be encouraged to remain on ticagrelor with an outpatient prescription to measure secondary outcomes.

Flow Chart

Patient's EMR will be reviewed at 30 days and at 1 year to document any primary or secondary outcome measures. Duration of the study is one year.

Data collection

Baseline Characteristics	Procedure Related information	Post-procedure Related Information
Gender		
Body mass index, kg/m ²	Consenting	PRU 1 hour
Current smoker	Randomization	PRU 4 hours
Hypertension	Baseline PRU test	Length of stay
Diabetes mellitus	Loading dose administration	Date of death
Dyslipidemia	Access (femoral, Radial)	Repeat MI
Prior coronary artery disease	Start catheterization	Stent thrombosis 30 days
Prior aspirin	Culprit vessel	CVA
Prior beta-blockers	Type of stent	Urgent Revascularization
Prior statins	Number of stents	
LVEF (%)	Fluoro time/dose	
Creatinine clearance, mL/min	Contrast volume	TIMI Minimal bleeding
Hemoglobin (gr/dl)	Narcotic use	TIMI Minor bleeding
Platelet count, 1,000/mm ³		TIMI Major bleeding
Low-density lipoprotein (mg/dl)		Access site complication (hematoma, pseudoaneurysm, need for surgical or percutaneous repair)
High-density lipoprotein (mg/dl)		

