Data will be collected by the personnel delegated by the PI. Preliminary data will be analyzed after enrollment of 65 patients.

Timeline /Schedule of events

	Visit 1 Baseline	Visit 2 Procedure	Visit 3 Post Procedure	Visit 4 Discharge	Visit 5 30 day follow up- (+/- 14 d) EMR-Chart review	Visit 6 1 yr follow up- (+/- 14 d) EMR-Chart review
Inclusion/ Exclusion	X					
Informed Consent Obtained	X					
Demographics, Medical History, Con Meds	X					
Angiography /PCI Procedure		X				
Blood draw for PRU	X baseline, 1-hour and 4- hour levels can be collected before coronary angiograp hy for patients admitted to hospital floor	X	1 h after PCI 4h after PCI			

	before procedure					
MAACE Event documentation				X	X	X

Statistical Analysis

Patient characteristics will be presented as proportions for categorical variables and mean \pm standard deviation (SD) and or Median [lower quartile (01) - upper quartile (03)] for continuous variables. Comparison of categorical variables for patients who will receive integral pill form of ticagrelor and the other the chewed form will be performed using the chi-square and Fisher's exact test while the two sample t test will be done to assess differences in continuous patient characteristics. Visual displays of event free Survival and cumulative incidence curves will be generated by the Kaplan-Meier approach and event free survival among groups compared using the log rank test. In addition to time point analysis, an alternating logistic regression (ALR) will be fitted to evaluate P2Y12 reaction units (PRU) levels at baseline (before LD), 1 hour, and 4 hours. Further analysis will entail fitting both univariate and multivariate Cox proportional-hazards models to examine the association between baseline characteristics and each of outcomes: In-stent thrombosis and restenosis, MACCE, and the need for repeat revascularization within 1-year separately. All analyses will be done using SAS Version 9.4 (SAS Institute, Cary, NC) and tests performed at a 5% level of significance.

Monitoring Plan

The goal of monitoring in this study is primarily to make sure that the primary data are collected and recorded properly and consenting process was done.

The Principal Investigator will be responsible for monitoring the safety environment of the participants, and will ensure that

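### Exclusion criterion 11 and part of criterion 10 name drug use that can only occur after randomisation, and the available text does not say such patients stay in the analysis

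*Combined protocol and SAP*

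**What the plan says.** All references are to the combined protocol and SAP.

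- **Exclusion criteria, item 10:** "Any use of GP IIb-IIIa inhibitors 48-hours before the procedure or any use during the procedure".
- **Exclusion criteria, item 11:** "Any use of Cangrelor during or after the procedure". This item has no pre-procedure part.
- **Exclusion criteria, item 15**, for contrast, looks back only: "Fibrinolytic use within past 48 hours".
- **Randomization:** "Patients will be randomized prior to PCI", 1:1 within the NSTE-ACS and stable CAD strata.
- **Timeline / Schedule of events:** the inclusion/exclusion check is marked at Visit 1 only, as is "Demographics, Medical History, Con Meds". Visit 2 is a single row, "Angiography /PCI Procedure". For PRU, the baseline, 1-hour and 4-hour "levels can be collected before coronary angiograp hy for patients admitted to hospital floor".
- **Data collection table:** narcotic use has a field; GP IIb-IIIa inhibitor and cangrelor use do not.
- **Follow-up:** the patient's "EMR will be reviewed at 30 days and at 1 year to document any primary or secondary outcome measures".
- **Statistical Analysis:** patients are described by the pill form they will receive. No analysis population is defined, and there is no rule for a patient who meets an exclusion after randomisation.
- **Monitoring Plan:** item a) concerns who is enrolled. Item f) asks for the reason for a withdrawal to be documented. Neither says who is analysed.

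**The concern.** An exclusion criterion should be decidable when the patient is entered. Criterion 11, and the second half of criterion 10, depend on what happens during or after the procedure. For PCI that is after allocation.

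Use of these drugs may be related to how well platelets are inhibited, which is what the two arms are meant to change. Dropping users could therefore select patients on a consequence of treatment, and the arms compared would no longer be those randomised.

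Two groups are most exposed. Floor patients may have both post-dose PRU samples before angiography, so a completed primary outcome could be set aside because of a later event. Complicated procedures may also be the ones in which these drugs are used, so removing them could take events out of MACCE and bleeding, where few are likely with 132 patients.

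**Working it through.** **Timing.**

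| Item | When it can be known |
|---|---|
| Criterion 10, use in the 48 hours before | At Visit 1, unless angiography is more than momentarily later |
| Randomisation | Before PCI |
| Criterion 10, use during the procedure | After randomisation if the procedure is PCI |
| Criterion 11, during or after the procedure | After randomisation if during PCI or later |
| 1-hour and 4-hour PRU, floor patients | May be before angiography, hence before the event |

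The 48-hour look-back in criterion 10 is not challenged.

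**Size.** The plan gives no figure that tests this point: it states n = 132, 1:1 allocation and a 5% level, but no SD, effect, event rate or rate of use of either drug. Apart from n and allocation (66 per arm), every input below is assumed.

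*PRU if users are excluded.* PRU is normal in each arm, with means 200 (integral) and 160 (chewed) and SD 80. The probability of use is logistic in PRU, with log-odds 0, 0.5, 1.0 or 1.5 per SD (odds ×1 to ×4.5), calibrated to 5% or 10% overall (132 × 0.05 = 6.6; 132 × 0.10 = 13.2; so 7-13 patients). The expected difference among non-users is found by numerical integration:

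| Log-odds per SD | 0 | 0.5 | 1.0 | 1.5 |
|---|---|---|---|---|
| 5% use | 40.0 | 39.5 | 38.4 | 37.1 |
| 10% use | 40.0 | 39.2 | 37.2 | 35.3 |

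SE = 80 × √(2/66) = 13.93. The largest shift is 4.72, and 4.72 / 13.93 = 0.34 SE.

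Over SD 60, 80, 100 and true difference 20, 40, 60, with log-odds 0.5-1.5, the shift is 0.23-7.02 PRU. The largest ratio is 6.72 / 10.44 = 0.64 SE (SD 60, difference 60).

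*Unequal exclusion with no true difference.* The model above gives the arm no effect on use except through PRU. A separate simulation (20,000 replicates, log-odds 1 per SD) fixed different exclusion rates by arm. Excluding 10% of integral and 5% of chewed patients shifts the difference by about 0.04 SD (type I error about 5.7%). At 15% and 5% the shift is about 0.08 SD (about 7.4%). Both shifts go against chewing. Equal 5% exclusion gives essentially none (about 4.9%).

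*PRU if users are kept.* Set users' post-drug PRU to 50, 100 or 150, for half or all users. Over the 48 combinations the observed difference is 25.3-39.0 instead of 40. It is further from 40 than exclusion in 46 of the 48; the other two are near-ties. If instead half of users' values are treated as missing, with log-odds 0.5-1.5, the difference is 37.9-39.8.

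*MACCE.* With an assumed event rate of 5-15%, 132 patients give 6.6-19.8 events. Share carried by users = use × RR / (use × RR + 1 − use). With 5% use and RR 1 this is 0.05; with 10% use and RR 3 it is 0.30 / 1.20 = 0.25. Events at risk of being lost run from 0.05 × 6.6 = 0.33 to 0.25 × 19.8 = 4.95. This is a count of lost events, not a between-arm bias.

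**The case against.** The strongest reply is that exclusion criteria govern entry. The check is ticked only at Visit 1, the Monitoring Plan speaks of enrolment, and nothing tells anyone to re-apply the list later or to drop data. The chart review at 30 days and 1 year makes no exception for users of these drugs. This stands: a reader might infer that the trial plans to remove such patients, and the documents do not say so. The harm is conditional on literal application.

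Other limits also stand. The procedure is not defined, and the schedule puts angiography and PCI in one row, so use during diagnostic angiography could precede randomisation. Planned use may have been meant, although the text says any use and criterion 15 shows that a backward-looking rule could be written. A figure is not shown and might address handling. The missing analysis set affects every patient, not only these. Chart review might recover use despite the absent fields.

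A reader might also infer that PRU results would be seriously biased, or that exclusion would favour chewing. Neither follows. The PRU effect is small under the base assumptions and zero if use is unrelated to PRU. The modelled shifts shrink a benefit of chewing or run against it, though that reassurance depends on the models chosen.

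Nor does it follow that keeping all observed PRU values is the better primary analysis. Under these assumptions that usually attenuates more than exclusion does. Whether PRU measured after another antiplatelet drug should count is a choice of estimand.

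None of this answers the core point: two stated exclusions cannot be decided at entry, and nothing available says what happens when they are met later.

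**Conclusion.** The point holds as a defect of wording and a gap in handling. For use during PCI or later, criterion 11 and the second half of criterion 10 describe post-randomisation events. Applied literally they would remove randomised patients, and the available text defines no analysis set that would prevent it.

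The size of any bias cannot be derived from the documents. Under the assumed inputs the PRU shrinkage is 0-4.7 in the base case and at most 0.64 SE over the wider grid; about 0.3 to 5 MACCE events could be lost. The main risk is to the randomised comparison and to scarce MACCE and bleeding events, not to the PRU estimate. Low to moderate severity, medium confidence: worth correcting because it is cheap.

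**What to change.** 1. Limit criteria 10 and 11, as eligibility rules, to use or planned use known before randomisation.
2. State that all randomised patients stay in the MACCE and bleeding analyses by assigned arm, and that no PRU sample drawn before such a drug is discarded.
3. Add fields for GP IIb-IIIa inhibitor and cangrelor use, with time, to the data collection table, and report use by arm.
4. For PRU samples drawn after such a drug, pre-specify the handling and report results both with those values and with them treated as missing. Which is primary is for the sponsor to choose and justify. Treating them as missing does not by itself remove the selection.

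Cost: protocol and SAP wording, a few data fields and one extra analysis. Some PRU values may reflect another antiplatelet drug, which is why both results are needed. No change to the clinical use of either drug is proposed.

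### Exclusion 10 counts its 48-hour GP IIb-IIIa window back from the procedure, so it does not assure 48 drug-free hours before PRU draws taken on the floor ahead of the procedure

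*Combined protocol and SAP*

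**What the plan says.** Exclusion criteria, item 10, excludes patients with "Any use of GP IIb-IIIa inhibitors 48-hours before the procedure or any use during the procedure". The Timeline/Schedule of events lists "Angiography /PCI Procedure" under Visit 2, so the procedure is the angiography or PCI itself.

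The primary outcome is timed from a different event. Primary Outcome Measures defines it as PRU, and the percentage of patients with PRU above 208, at 1 hour and 4 hours after the ticagrelor loading dose.

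For NSTE-ACS inpatients the dose can come well before the procedure. Study procedures says "These patients often receive the loading dose of 180mg ticagrelor on the medical floor", that "the baseline PRU level blood draw, can be obtained on the floor before that loading dose is administered", and that "The subsequent 1-hour and 4-hour blood draws can be obtained on the medical floor or in catheterization suite". The Schedule of events adds that, for patients already on the hospital floor, the baseline, 1-hour and 4-hour "levels can be collected before coronary" angiography.

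No section limits the time from floor loading to the procedure, and no other exclusion ties GP IIb-IIIa use to the loading dose or the blood draws.

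**The concern.** A GP IIb-IIIa inhibitor is another antiplatelet drug. The neighbouring exclusions for chronic P2Y12 therapy (item 3) and cangrelor (item 11), together with the PRU endpoint, suggest that item 10 is there at least partly to keep other agents out of the platelet readings. That purpose is an inference; the protocol does not state it.

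On that reading the window hangs on the wrong event for floor-loaded patients. The procedure can follow the whole primary measurement, so a patient who satisfies item 10 may have had less than 48 drug-free hours when PRU was measured. Elective patients are dosed close to the procedure, so the two strata are screened to different effective standards.

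Two practical problems follow.

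- Eligibility is checked at Visit 1, when a floor patient's procedure is still ahead. Compliance with item 10 can be settled only after randomization and dosing, and possibly after all draws. Monitoring Plan item (a) nevertheless promises that only eligible subjects are enrolled.
- The clause on use during the procedure can make a floor-loaded patient ineligible after the 4-hour draw, the point at which the protocol regards the primary outcome as complete.

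**Working it through.** The plan gives no figure of its own to reproduce here. The check is interval arithmetic on its timing rules.

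**Inputs**
- Window: 48 h, counted back from the procedure (Exclusion criteria, item 10).
- Draw times after the loading dose: t = 0 (baseline, taken as coinciding with the dose), 1 h and 4 h (Primary Outcome Measures).
- L, hours from floor loading dose to procedure: not given and not capped. It is an assumption, shown over 4 to 72 h.

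**Formula**
A draw at t falls L - t hours before the procedure. Item 10 allows use only more than 48 h before the procedure. The drug-free time it assures before a draw is therefore

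max(0, 48 - (L - t)), for draws no later than the procedure (t ≤ L).

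Example with L = 24 h: baseline 48 - 24 = 24 h; 1-hour draw 48 - 23 = 25 h; 4-hour draw 48 - 20 = 28 h.

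| Assumed L (h) | Before baseline (h) | Before 1-hour draw (h) | Before 4-hour draw (h) |
|---|---|---|---|
| 4 | 44 | 45 | 48 |
| 6 | 42 | 43 | 46 |
| 12 | 36 | 37 | 40 |
| 24 | 24 | 25 | 28 |
| 36 | 12 | 13 | 16 |
| 48 | 0 | 1 | 4 |
| 49 | 0 | 0 | 3 |
| 52 | 0 | 0 | 0 |
| 72 | 0 | 0 | 0 |

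**Where it reaches zero**
Setting 48 - (L - t) = 0 gives L = 48 + t: 48 h for baseline, 49 h for the 1-hour draw and 52 h for the 4-hour draw. Above 52 h, even use between the loading dose and the 4-hour draw would pass item 10.

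**Effect of the draw windows**
The elective paragraph of Study procedures allows 1 h ± 60 min and 4 h ± 90 min. If these also apply on the floor, the 1-hour draw falls at 0 to 2 h and the 4-hour draw at 2.5 to 5.5 h. The zero points become 48 to 50 h and 50.5 to 53.5 h.

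**Elective stratum for comparison**
There the later draws follow the procedure, and the first is due at most 1 h + 60 min = 2 h after the dose. The dose can then precede the procedure by at most 2 h, so at least 48 - 2 = 46 h is assured before it. No comparable bound exists for floor-loaded patients.

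**The case against.** The case for leaving item 10 alone has several parts.

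*Zero is remote.* Drawing PRU before the procedure does not by itself remove the washout. A reader might infer that it does, or that a lag of 48 h already permits use through the 4-hour draw. Neither follows. At L = 48 h, use after the dose still falls within 48 h of the procedure and is excluded; permission through the 4-hour draw needs 52 h. At L of 24 h or less, at least 25 h remains before either primary draw. Floor draws are also optional, since the catheterization suite is allowed. All of this stands.

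*No bias between arms.* A reader might infer a bias towards no difference. Randomization is 1:1 within strata, so prior use should be balanced apart from chance, and unequal screening between strata does not itself distort chewed versus integral. Some dilution is plausible, but nothing in the protocol lets its size be shown. This stands too. A suppressed baseline might also be noticed, because baseline PRU is measured in everyone.

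*The purpose may be different.* TIMI bleeding is a secondary outcome, so a procedure-based window might serve bleeding safety. That is possible, and it bears on how item 10 is rewritten. It does not supply the missing protection for PRU.

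*Screening is partly possible.* Concomitant medications are taken at Visit 1, so known use can be compared with a planned procedure time. Use after Visit 1 cannot be, and a planned time can move. Clauses about use during or after the procedure have this limitation in both strata, but only in floor-loaded patients can such a clause act after all the primary readings are taken.

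The mismatch between item 10 and the floor-loading provisions survives these points.

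**Conclusion.** The concern holds as a gap in the eligibility rule. In a route that the protocol itself describes as common, item 10 does not assure 48 drug-free hours before the primary measurement. Any lag above 4 h leaves both primary draws short of 48 h whenever they are taken before the procedure. The shortfall equals the interval from draw to procedure. For these patients the item also cannot be fully checked at Visit 1.

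The size depends on L, which the documents neither give nor limit. Zero is therefore an extreme that is not excluded; it is not a demonstrated feature of the trial.

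A reader might also try to count affected patients, for instance by applying an assumed rate of use to half of the 132. The documents give neither the rate nor the split between strata. Only patients who were floor-loaded, drawn before the procedure and recently exposed would count, and a shortened interval does not make a reading uninterpretable. No count can be supported.

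The likely consequence is distorted or noisier PRU in the NSTE-ACS stratum, together with eligibility failures discovered after measurement. This rests on item 10 being meant, at least in part, to protect PRU.

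**What to change.** Reconcile item 10 with the floor-loading and blood-draw provisions:

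- Count the existing 48 hours back from the baseline PRU draw, in both strata, and check it at Visit 1. Item 15, on fibrinolytics, is already worded so that it can be checked at screening. No change to the length of the window is proposed.
- Add a data field for the date and time of any later GP IIb-IIIa use, including use after the 4-hour draw and during the procedure. The Data collection table has no such field, and concomitant medications are scheduled only at Visit 1. Without the field, use between the 4-hour draw and the procedure would be neither excluded nor recorded once the reference point moves.
- Treat use between the loading dose and the 4-hour draw as a post-randomization event, not as an eligibility failure. Keep those patients in the main analysis and add a sensitivity analysis of PRU without the affected readings.
- Revise the clause on use during the procedure to agree with this. If the sponsor intends item 10 to serve a safety purpose as well, that purpose should be stated separately; whether it calls for a procedure-based rule is a clinical matter not judged here.

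The cost is a wording amendment, one data field and one sensitivity analysis, with no extra visits, tests or patients. A few floor-loaded patients with recent use would become ineligible.
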